Grade 4	Permanently discontinue blinatumomab.	Give methylprednisolone 2 mg/kg IV once then prednisone 1-2 mg/kg oral daily with taper over at least 4 weeks after resolution to ≤ Grade 1. Permanently discontinue pembrolizumab.
*Patients requiring a delay of blinatumomab > 14 days due to toxicity should go off protocol therapy.		

Other Non-Hematologic Adverse Reactions Despite Optimal Supportive Care	Management for Blinatumomab	Management for Pembrolizumab
Grade 1 or 2	Continue infusion.	No change in dose
Grade 3	Withhold* until < Grade 2 then resume blinatumomab at 9 mcg/day. Escalate to 28 mcg/day after 7 days if the toxicity does not recur. If Grade 3 toxicity recurs despite optimal supportive care, permanently discontinue blinatumomab.	Withhold* until < Grade 2 then resume at same dose. Missed doses are not made up. If Grade 3 toxicity recurs despite optimal supportive care, permanently discontinue pembrolizumab.
Grade 4	Permanently discontinue blinatumomab.	Permanently discontinue pembrolizumab.
*Patients requiring a delay of next cycle by >14 days due to toxicity should go off protocol therapy.		

For additional toxicity management guidance please reference Brahmer et al, “Management of immune-related adverse events in patients treated with immune checkpoint inhibitor therapy: ASCO clinical practice guideline” in JCO Feb 2018; the NCCN guidelines for “Management of Immunotherapy-related toxicities”); and the SITC guidelines by Puanov et al, “Managing toxicities associated with immune checkpoint inhibitors: consensus recommendations from the SITC toxicity management working group” in JITC Nov 2017.

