5.7.1 Management of non-Hematologic Toxicities

As Blinatumomab is an approved treatment for this indication, reducing or withholding pembrolizumab should be considered as the first option in response to a toxicity prior to adjusting the Blinatumomab dosing.

Any Grade 3 or severe AE that recurs should lead to permanent discontinuation of pembrolizumab, as should any persistent grade 2 or 3 AE (excluding endocrinopathies) that do not recover to grade 1 within 12 weeks of the last dose of pembrolizumab.

Cytokine Release Syndrome	Management for Blinatumomab	Management for Pembrolizumab
Grade 1 -Fever -Constitutional symptoms	Continue infusion. Vigilant supportive care. Assess for infection.	No change in dose. Patient should be admitted for subsequent pembrolizumab dose given in combination with blinatumomab and monitored for at least 72 hours after pembrolizumab administration.
Grade 2 -Hypotension responsive to fluids or one low dose pressor** -Hypoxia: reponds to <40% O ₂ -Organ toxicity: Grade 2	Continue infusion. Vigilant supportive care. Assess for infection.	No change in dose. Patient should be admitted for subsequent pembrolizumab dose given in combination with blinatumomab and monitored for at least 72 hours after pembrolizumab administration.
Grade 3 -Hypotension requiring multiple pressors or high dose pressors** -Hypoxia requiring ≥40% O ₂	Withhold* until resolved then resume blinatumomab at 9 mcg/day. Escalate to 28 mcg/day after 7 days if the toxicity does not recur.	Stop Infusion. Additional appropriate medical therapy may include but is not limited to: IV fluids

Cytokine Release Syndrome	Management for Blinatumomab	Management for Pembrolizumab
-Organ toxicity: Grade 3 or Grade 4 transaminitis	Vigilant supportive care. Assess for infection. Consider administration of corticosteroids and/or tocilizumab.	Antihistamines NSAIDS Acetaminophen Narcotics Oxygen Vasopressors Corticosteroids Tocilizumab Increase monitoring of vital signs as medically indicated until the subject is deemed medically stable in the opinion of the investigator. Hospitalization may be indicated. Subject is permanently discontinued from further trial treatment administration.

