Grade 2	Refer to CRS section above.	
Stop Infusion and monitor symptoms.
 
Additional appropriate medical therapy may include but is not limited to:
 
 IV fluids Antihistamines NSAIDS Acetaminophen Narcotics 
Increase monitoring of vital signs as medically indicated until the subject is deemed medically stable in the opinion of the investigator.
 
If symptoms resolve within one hour of stopping drug infusion, the infusion may be restarted at 50% of the original infusion rate (e.g., from 100 mL/hr to 50 mL/hr). Otherwise dosing will be held until symptoms resolve and the subject should be premedicated for the next scheduled dose.
 
Withhold until ≤ Grade 1.
 
Premedicate subsequent administration with hydrocortisone 100 mg IV once, diphenhydramine 50 mg IV or per oral (or equivalent alternate antihistamine), Tylenol 650 mg per oral.
 
Subjects who develop Grade 2 toxicity despite adequate premedication permanently discontinue pembrolizumab.

Grade 3
	
Refer to CRS section above.
	
Stop Infusion. Additional appropriate medical therapy may include but is not limited to: IV fluids Antihistamines NSAIDS Acetaminophen Narcotics Oxygen Pressors Corticosteroids Epinephrine
 
Increase monitoring of vital signs as medically indicated until the subject is deemed medically stable in the opinion of the investigator. Hospitalization may be indicated.
 
Subject is permanently discontinued from further trial treatment administration.

Grade 4
	
Refer to CRS section above.
	
Stop Infusion. Additional appropriate medical therapy may include but is not limited to: IV fluids Antihistamines NSAIDS Acetaminophen Narcotics Oxygen Pressors Corticosteroids Epinephrine
 
Increase monitoring of vital signs as medically indicated until the subject is deemed medically stable in the opinion of the investigator. Hospitalization may be indicated.
 
Subject is permanently discontinued from further trial treatment administration.

*Patients requiring a delay of blinatumomab >14 days due to toxicity should go off protocol therapy. Appropriate resuscitation equipment should be available in the room and a physician readily available during the period of drug administration.
		

Pneumonitis	Management for Blinatumomab	Management for Pembrolizumab
≤ Grade 1	No change in dose	No change in dose.

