Grade 3	
Withhold* until resolved to ≤ Grade 1 then resume blinatumomab at 9 mcg/day. Escalate to 28 mcg/day after 7 days if the toxicity does not recur. If diarrhea/colitis recurs then permanently discontinue blinatumomab.
	
Start prednisone 1-2 mg/kg oral daily with taper over at least 4 weeks after resolution to ≤ Grade 1.
 
Withhold pembrolizumab until ≤ Grade 1. Missed doses are not made up.
 
If colitis recurs at Grade 3 or higher despite corticosteroids permanently discontinue pembrolizumab.
 
If Grade 3 lasting >1 week despite oral prednisone, administer IV corticosteroids followed by high-dose oral corticosteroids per institutional standard.
 
Permanently discontinue pembrolizumab.

Grade 4	Permanently discontinue blinatumomab.	
Start prednisone 1-2 mg/kg oral daily with taper over at least 4 weeks after resolution to ≤ Grade 1. If Grade 3 lasting >1 week despite oral prednisone, administer IV corticosteroids followed by high-dose oral corticosteroids per institutional standard.
 
Permanently discontinue pembrolizumab.

*Patients requiring a delay of blinatumomab >14 days due to toxicity should go off protocol therapy.
		

Nephritis	Management for Blinatumomab	Management for Pembrolizumab
≤ Grade 1	No change in dose	No change in dose.
Grade 2	No change in dose	Withhold until ≤ Grade 1. Missed doses are not made up. Start prednisone 1-2 mg/kg oral daily with taper over at least 4 weeks after resolution to ≤ Grade 1. If nephritis recurs at Grade 2 or higher despite corticosteroids then permanently discontinue pembrolizumab.
Grade 3	Withhold* until resolved to ≤ Grade 1 then resume blinatumomab at 9 mcg/day. Escalate to 28 mcg/day after 7 days if the toxicity does not recur. If nephritis recurs then permanently discontinue blinatumomab.	Start prednisone 1-2 mg/kg oral daily with taper over at least 4 weeks after resolution to ≤ Grade 1. Permanently discontinue pembrolizumab.
Grade 4	Permanently discontinue blinatumomab.	Start prednisone 1-2 mg/kg oral daily with taper over at least 4 weeks after resolution to ≤ Grade 1. Permanently discontinue pembrolizumab.
*Patients requiring a delay of blinatumomab > 14 days due to toxicity should go off protocol therapy.		

Hypophysitis	Management for Blinatumomab	Management for Pembrolizumab
≤ Grade 1	No change in dose	No change in dose.

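### Section 5.7.1 gives stop/continue instructions that cannot all be followed for Grade 3 CRS, Grade 3 infusion reactions and Grade 3 colitis

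*Combined protocol and SAP*

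**What the plan says.** All three rows are in Section 5.7.1 (Management of non-Hematologic Toxicities).

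- **CRS, Grade 3.** Blinatumomab column: "Withhold* until resolved then resume blinatumomab at 9 mcg/day", then "Escalate to 28 mcg/day after 7 days if the toxicity does not recur". Pembrolizumab column: stop the infusion, give supportive treatment, and finally "Subject is permanently discontinued from further trial treatment administration".
- **Infusion reactions, Grade 3.** Blinatumomab column: "Refer to CRS section above". The pembrolizumab column ends with the same sentence on trial treatment as the CRS row.
- **Diarrhea/colitis, Grade 3, pembrolizumab column.** The cell gives "Withhold pembrolizumab until ≤ Grade 1. Missed doses are not made up", then "If colitis recurs at Grade 3 or higher despite corticosteroids permanently discontinue pembrolizumab". It goes on to Grade 3 events lasting more than a week despite oral prednisone, and closes with a permanent stop of pembrolizumab to which no condition is attached.

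**The concern.** In the CRS row, one column has the patient going back on blinatumomab and the other ends trial treatment. Blinatumomab is one of the trial treatments, so on a literal reading the two cells exclude each other. In the colitis cell, if the closing line governs every Grade 3 event, the withhold and recurrence instructions above it have no use. If they govern, the closing line is wrong or is missing its condition.

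The study runs at several centers. Two sites facing the same severe event could each follow the table and do opposite things: one stops a drug for good, the other restarts it. At stake are patient safety and uniform conduct.

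**Working it through.** The plan states no figure on this point, so the check is a comparison of text.

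**1. Is the CRS sentence limited to pembrolizumab by its wording?** Where the tables mean one drug, they can name it. The Grade 2 infusion-reaction cell, in the same pembrolizumab column, reads "Subjects who develop Grade 2 toxicity despite adequate premedication permanently discontinue pembrolizumab". The pembrolizumab guidance in Appendix G (Section 3.11) uses the broad trial-treatment wording for Grade 2 as well as for Grades 3 and 4. The protocol therefore narrowed the Grade 2 sentence to pembrolizumab and left the Grade 3 and 4 sentences broad. A site may read that difference as deliberate.

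**2. Do the infusion-reaction rows conflict?** Assume that the cross-reference to the CRS table is read grade for grade.

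- Grade 3: the blinatumomab cell leads to withhold and resume; the pembrolizumab cell ends trial treatment. Conflict.
- Grade 4: the blinatumomab cell leads to Grade 4 CRS, where both columns take the patient off protocol therapy. No conflict.

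**3. Can the colitis instructions be applied together?** The first two can: withhold, then stop permanently if Grade 3 or higher recurs. They also agree with the general recurrence rule at the head of Section 5.7.1. The closing line is what breaks the sequence. The same words, "permanently discontinue pembrolizumab", stand without a condition as the actual rule for Grade 4 colitis and, in substance, for Grade 3 pneumonitis and nephritis. A site has grounds to read them that way here too.

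**4. Does another part of the document settle it?** Appendix G (Section 3.2) holds pembrolizumab for Grade 3 colitis and stops it permanently for Grade 4. But its overview sends any dose-modification question back to the protocol, so it cannot override Section 5.7.1.

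**5. How often might the CRS row be used?** Section 1.2.1 gives 1.3% Grade 3 or higher CRS with blinatumomab. For 24 patients:

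- expected events: 24 × 0.013 = 0.31
- chance of at least one: 1 − 0.987^24 = 1 − 0.73 = 0.27

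This is illustrative only. The rate includes Grade 4, and the documents give no rate for the combination. They link CRS to high disease burden, and this trial requires more than 50% marrow lymphoblasts, so 1.3% may be too low here.

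**The case against.** The strongest reply is that the CRS sentence means pembrolizumab only. It sits in a column headed for that drug. Its wording matches the Grade 3 and 4 infusion-reaction text of the pembrolizumab guidance in Appendix G, so it looks carried over. When both drugs stop for CRS, the Grade 4 row says so in both columns, which the Grade 3 row does not. Sections 5.7 and 5.7.1 also say to consider adjusting pembrolizumab before blinatumomab. All of this stands, and it makes the narrow reading plausible. It also means that a flat order to stop all treatment should not be read into the sentence as certain. It does not make the narrow reading explicit, and the narrowed Grade 2 sentence points the other way.

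For colitis, the closing line follows directly on the sentence about Grade 3 lasting more than a week, and may belong to it. The layout of a table extracted from PDF is weak evidence either way. But as the text stands the line carries no such condition.

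A reader might go further and infer damage to the primary analysis: a patient stopped early becomes a non-responder, and one response (1/24 = 4.2 points) can separate 10 from the 11 needed to reject the null hypothesis. The documents do not support that:

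- Under Section 10.4, patients are evaluable for response only if they receive the combination from Day 15 of Cycle 1. A patient who never starts pembrolizumab because of earlier CRS is outside that set, and the pembrolizumab cell stops that drug on either reading.
- A patient stopped after Day 15 can still have a response recorded: Section 3.1.1 counts response after 1 or 2 cycles, and Section 5.1.6 schedules a marrow at Cycle 1 Day 29 + 8 days.
- Section 7.1.1 further limits response evaluability to patients with at least one cycle and a re-evaluation.

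The 4.2 points are also the weight of any single patient for any reason.

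**Conclusion.** The instructions need reconciling in three places: the Grade 3 CRS row, the Grade 3 infusion-reaction row, and the Grade 3 diarrhea/colitis cell for pembrolizumab. The Grade 4 infusion-reaction row is consistent. For CRS the finding rests on a literal reading of a sentence that has a plausible narrower meaning; for colitis it rests on a closing line that carries no condition.

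The size is qualitative: opposite stop/continue decisions are possible for the same severe event. No effect on the overall response rate is shown.

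A reader might also infer that the count of dose-limiting toxicities (DLTs) is affected, because Section 5.1.4 exempts short Grade 3 CRS but counts toxicity that blocks the next dose for more than 14 days. Pembrolizumab stops on both readings of the CRS row, so for that drug the question does not turn on this conflict. Grade 3 colitis is not among the listed exceptions, so if attributed as the definition requires it is a DLT whichever instruction applies.

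**What to change.** Reconcile the two columns of the Grade 3 CRS row, and the Grade 3 infusion-reaction row that depends on it, so that each says by name which drug or drugs stop and which may resume. Reconcile the Grade 3 diarrhea/colitis cell so that withholding, stopping on recurrence and the closing permanent stop each apply to a stated condition. The clinical rule is for the sponsor to decide; this review takes no view on it.

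The cost is a wording amendment. Section 11.10 requires IRB approval before it is implemented. Sample size, endpoints and analysis do not change.

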5.1.4 Stage I – Dose limiting toxicity definition and stopping rules

To determine the safety of pembrolizumab in combination with blinatumomab in patients with acute lymphoblastic leukemia, the combination will be administered to 3-6 patients with relapsed or refractory B-lineage acute lymphoblastic leukemia.

Toxicity will be graded according to the National Cancer Institute (NCI) Common Toxicity Criteria for Adverse Events (CTCAE) version 4.03. Adverse events will be assessed continuously throughout therapy.

Dose Limiting Toxicity (DLT) is defined as a clinically significant adverse event that is considered by the investigator to be probably or definitely related to pembrolizumab or the combination of pembrolizumab and blinatumomab occurring within 42 days of the first dose of pembrolizumab on Day 15 of Cycle 1 as follows:

- Any Grade 3-5 non-hematologic toxicity EXCEPT:
 - Grade 3 cytokine release syndrome that resolves in 7 days or less
 - Grade 3 neurotoxicity that resolves in 7 days or less
 - Grade 3 infections
 - Grade 3 or 4 febrile neutropenia unless deemed by investigator to be definitely related to pembrolizumab
 - Grade 3 or 4 laboratory abnormalities unless they warrant temporary discontinuation of pembrolizumab or permanent discontinuation of blinatumomab (see tables, 5.7.1 and 5.7.2)
 - Grade 3 or 4 lymphopenia
- Any clinically significant toxicity that precludes administration of the next scheduled dose for more than 14 days

Decision to proceed to Stage 2 of the study will be made as follows below.

Number of Patients with DLT	Decision Rule
0 out of 3	Proceed to Stage 2 of study.
1 out of 3	Enter at least 3 more patients. 
 If 0 of these 3 patients experience DLT, proceed to Stage 2 of study If 1 or more of this group suffer DLT, then study will be placed on hold. Decision regarding dosing of pembrolizumab and continuation of study will be made after discussion between sponsors and investigators.
≥ 2	Study will be placed on hold and the FDA notified. Decision regarding dosing of pembrolizumab and continuation of study will be made after discussion between sponsors, investigators and FDA.
≤ 1 out of 6	Proceed to Stage 2 of study.

Subjects withdrawing from investigational treatment during the DLT monitoring period for a reason that is definitely unrelated to toxicity of the study agent (e.g. disease progression, patient withdrawal of consent) will be replaced.

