5.4 Prohibited concomitant therapy

Except as described in the protocol, **corticosteroids** are prohibited for any indication given the anti-leukemic activity of these agents interfering with interpretation of the study results.

Corticosteroids are permitted to prevent or treat infusion reactions and cytokine release syndrome or Events of Clinical Interest (ECI, See appendix G). Topical or inhaled steroids are

permitted.

Use of **G-CSF** or **GM-CSF** is prohibited.

Any other potentially anti-neoplastic therapy is prohibited regardless of indication for administration.

Any biologic, antibody, or immunomodulatory agent, except as described in the protocol, is prohibited.

Other investigational therapies must not be used while the patient is on the study. Anticancer therapy (chemotherapy, biologic or radiation therapy, and surgery) other than the study treatments must not be given to patients while the patient is on the study medication. If such agents are required for a patient then the patient must be removed from the study.

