Grade 4 -Mechanical ventilation -Organ toxicity: Grade 4 excluding transaminitis	Off protocol therapy. Vigilant supportive care. Assess for infection. Consider administration of corticosteroids and/or tocilizumab..	Off protocol therapy. Vigilant supportive care. Assess for infection. Consider administration of corticosteroids and/or tocilizumab..

*Patients requiring a delay of blinatumomab >14 days should go off protocol therapy.
 
**High-dose pressors include the following administered for ≥3 hours: norepinephrine ≥20 mcg/min, dopamine ≥10 mcg/kg/min, phenylephrine ≥200 mcg/min, epinephrine ≥10 mcg/min, if on vasopressin: vasopressin + norepinephrine equivalent of ≥10 mcg/min, if on combination of vasopressors: norepinephrine equivalent ≥20 mcg/min. NOREPINEPHRINE EQUIVALENT DOSE = [norepinephrine (mcg/min)] + [dopamine (mcg/kg/min)/2] + [epinephrine (mcg/min)] + [phenylephrine (mcg/min)/10]/
		

Neurologic Toxicity	Management for Blinatumomab	Management for Pembrolizumab
Grade 1 or 2	Continue infusion.	No change in dose.
Grade 3	Withhold* until < Grade 2 for 3 days then resume blinatumomab at 9 mcg/day. Escalate to 28 mcg/day after 7 days if the toxicity does not recur. If the toxicity occurred at 9 mcg/day or takes more than 7 days to improve to <Grade 2 then patient goes off protocol therapy.	Withhold* until < Grade 2 then resume at same dose. Missed doses should be given as close to missed scheduled dose as possible. Subsequent doses are given every 3 weeks.
Grade 4	Off protocol therapy	Off protocol therapy
Seizure, Grade 1 or 2	Withhold* until resolved and institute anticonvulsant prophylaxis (neurology consultation)	Withhold until resolved then resume at same dose. Missed doses should be given as close to

Neurologic Toxicity	Management for Blinatumomab	Management for Pembrolizumab
	recommended) then resume blinatumomab at 9 mcg/day. Escalate to 28 mcg/day after 7 days if the toxicity does not recur.	missed scheduled dose as possible. Subsequent doses are given every 3 weeks until completion of planned cycles of therapy.
Seizure, Grade 3 or 4 or recurrent Grade 1 or 2	Off protocol therapy.	Off protocol therapy.
*Patients requiring a delay of blinatumomab >14 days should go off protocol therapy.		

Infusion Reactions	Management for Blinatumomab	Management for Pembrolizumab
≤ Grade 1	Refer to CRS section above.	Increase monitoring of vital signs as needed until clinical stability confirmed. No change in dose.

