Grade 4	Permanently discontinue blinatumomab.	Withhold of permanently discontinue pembrolizumab Treat with non-selective beta-blockers (eg. Propranolol) and/or thionamides as appropriate Monitor for signs and symptoms of the disorders
*Patients requiring a delay of blinatumomab > 14 days due to toxicity should go off protocol therapy.		

Immune-mediated hypothyroidism	Management for Blinatumomab	Management for Pembrolizumab
≤ Grade 1	No change in dose	No change in dose
Grade 2	No change in dose	No Change in dose Initiate thyroid replacement hormones (eg, levothyroxine or liothyronine) per standard of care Monitor for signs and symptoms of thyroid disorders.
Grade 3	Withhold* until resolved to ≤ Grade 1 then resume blinatumomab at 9 mcg/day. Escalate to 28 mcg/day after 7 days if the toxicity does not recur. If immune-mediate hypothyroidism recurs then permanently discontinue blinatumomab.	No change in dose Initiate thyroid replacement hormones (eg, levothyroxine or liothyronine) per standard of care Monitor for signs and symptoms of thyroid disorders.
Grade 4	Permanently discontinue blinatumomab.	No change in dose Initiate thyroid replacement hormones (eg, levothyroxine or liothyronine) per standard of care Monitor for signs and symptoms of thyroid disorders.
*Patients requiring a delay of blinatumomab > 14 days due to toxicity should go off protocol therapy.		

Other Immune-mediated Adverse Reactions	Management for Blinatumomab	Management for Pembrolizumab
≤ Grade 1	No change in dose	No change in dose
Grade 2	No change in dose	Withhold until ≤ Grade 1. Missed doses are not made up. Start prednisone 1-2 mg/kg oral daily with taper over at least 4 weeks after resolution to ≤ Grade 1. If immune-mediated reaction recurs at Grade 2 or higher despite corticosteroids then permanently discontinue pembrolizumab.
Grade 3	Withhold* until resolved to ≤ Grade 1 then resume blinatumomab at 9	Give methylprednisolone 2 mg/kg IV once then prednisone 1-2

Other Immune-mediated Adverse Reactions	Management for Blinatumomab	Management for Pembrolizumab
	mcg/day. Escalate to 28 mcg/day after 7 days if the toxicity does not recur. If immune-mediate reaction recurs then permanently discontinue blinatumomab.	mg/kg oral daily with taper over at least 4 weeks after resolution to ≤ Grade 1. Permanently discontinue pembrolizumab.

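### Two Section 5.7.1 tables fit an immune-mediated neurologic event: after a first Grade 3 event improving within 7 days, one resumes pembrolizumab while the other, and Appendix G 3.6, stop it

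*Combined protocol and SAP*

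**What the plan says.** Section 5.7.1 sets out non-hematologic toxicity management table by table.

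- **Neurologic Toxicity table** (no limit by cause; seizures have their own rows). At Grade 1 or 2 pembrolizumab is unchanged. At Grade 3 the pembrolizumab column reads "Withhold* until < Grade 2 then resume at same dose. Missed doses should be given as close to missed scheduled dose as possible", and no corticosteroid is directed. The blinatumomab column adds a limit: "If the toxicity occurred at 9 mcg/day or takes more than 7 days to improve to <Grade 2 then patient goes off protocol therapy". At Grade 4 both drugs end.
- **Other Immune-mediated Adverse Reactions table** (no limit by organ). At Grade 2, for pembrolizumab: "Withhold until ≤ Grade 1. Missed doses are not made up. Start prednisone 1-2 mg/kg oral daily with taper over at least 4 weeks". At Grade 3 it gives one intravenous dose of methylprednisolone, then prednisone 1-2 "mg/kg oral daily with taper over at least 4 weeks after resolution to ≤ Grade 1. Permanently discontinue pembrolizumab".
- **Opening text of Section 5.7.1**: "Any Grade 3 or severe AE that recurs should lead to permanent discontinuation of pembrolizumab".
- **Appendix G 3.6** names the four neurologic events as Events of Clinical Interest at any grade. At Grade 2 it asks the physician to consider withholding pembrolizumab and to consider prednisone. At Grades 3 and 4 it discontinues pembrolizumab and gives systemic corticosteroids. The Appendix G overview defines discontinuation as permanent.

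**The concern.** An immune-mediated neuropathy or myasthenic syndrome is both a neurologic toxicity and an immune-mediated reaction, so an investigator can reasonably open either table. For a Grade 3 event that settles quickly, one table restarts pembrolizumab at full dose and the other ends it for good. Two sites following the same protocol could therefore treat the same event in opposite ways. A patient with Grade 3 Guillain-Barre or myasthenic syndrome could be re-exposed although the trial's own appendix says to stop. What is at stake is the safety of that patient and consistency between sites.

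**Working it through.** The plan states no figure on this point, so the check is a side-by-side reading for pembrolizumab in a non-seizure event listed in Appendix G 3.6.

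| Event | Neurologic Toxicity | Other Immune-mediated | Appendix G 3.6 | Result |
|---|---|---|---|---|
| Grade 2 | No change; no steroid directed | Withhold; doses not made up; prednisone with taper of at least 4 weeks | Consider withholding; consider prednisone | Differ |
| Grade 3, not at 9 mcg/day, below Grade 2 within 7 days | Resume same dose; missed doses given; no steroid directed | Steroids; permanent stop | Steroids; discontinue | Differ |
| Grade 3, over 7 days or at 9 mcg/day | Off protocol therapy | Permanent stop | Discontinue | Pembrolizumab ends in all |
| Grade 4 | Off protocol therapy | Permanent stop | Discontinue | Pembrolizumab ends in all |

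The 9 mcg/day condition rarely applies. Under Section 5.1.3 that dose is planned only for Days 1-7 of Cycle 1, before the first pembrolizumab dose on Day 15. After that it arises only on a restart following an interruption.

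**Search for a rule that chooses between the tables**

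1. Section 5.7 adjusts doses to the system with the worst grade. That ranks organ systems, not two tables for one event at one grade.
2. The opening of Section 5.7.1 stops pembrolizumab for a recurrent Grade 3 event, or for a Grade 2-3 event not recovered to Grade 1 within 12 weeks of the last dose. A first event that improves within 7 days meets neither condition.
3. Section 5.6 points to Appendix G for events related to pembrolizumab, but the Appendix G overview sends dose-modification questions back to the protocol. The two cross-references are circular.
4. The text after the Section 5.7.1 tables cites outside guidelines as additional guidance, without saying which table governs.

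**Size of the Grade 3 difference**

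- Scheduled doses (Section 5.1.3): 2 per cycle (Days 15 and 36) × 5 cycles = 10; 10 × 200 mg = 2,000 mg.
- Event after dose 1, Neurologic Toxicity table: 10 − 1 = 9 doses; 9 × 200 mg = 1,800 mg.
- Same event, Other Immune-mediated table: 0 doses.

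The 1,800 mg is a maximum. It requires an event straight after dose 1, no Grade 3 recurrence, a response, and all five cycles without relapse or transplant.

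**Frequency**

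The documents give none. Assuming, for illustration only, a per-patient probability p of any of the four events at any grade, the chance of at least one among 24 patients is 1 − (1 − p)^24:

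- p = 0.5%: 11.3%
- p = 1%: 21.4%
- p = 2%: 38.4%

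These figures include Grade 1, slow Grade 3 and Grade 4 events, for which pembrolizumab handling does not conflict. They do not measure the Grade 3 case at issue, which is rarer.

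**The case against.** The best defence is that *Other* is residual: the section runs through named tables and closes with two *Other* tables, so a neurologic event belongs to the Neurologic table. The DLT exception in Section 5.1.4 for "Grade 3 neurotoxicity that resolves in 7 days or less" fits that reading. The Appendix G overview also ranks the protocol first on dose modification and calls its own recommendations guidelines subject to clinical judgment.

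This is a fair reading, but it only selects the rule that resumes pembrolizumab, against Appendix G 3.6. The other reading is equally open: a separate table for other non-hematologic reactions follows, so *Other Immune-mediated* can mean immune reactions beyond the organ-specific ones already listed.

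Several parts of the defence stand and limit the point:

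- Sections 5.7 and 5.7.1 make reducing or withholding pembrolizumab the first option to consider for any toxicity. The end of Section 5.7.2 permanently stops the offending drug for toxicity below Grade 3 that requires cessation. With Appendix G asking only to consider withholding, Grade 2 is a matter of judgment. A reader might infer that two mandatory rules collide there with equal force; the documents do not support that.
- A reader might infer that the prednisone route breaches Section 5.4, where corticosteroids, outside protocol-described use, "are prohibited for any indication given the anti-leukemic activity of these agents interfering with interpretation of the study results". The same section goes on to permit them for Events of Clinical Interest, which covers all four events.
- Section 5.8 lets the investigator end treatment for an unacceptable event, and Section 8.8.1.2 requires assessment for these events before each dose.

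**Conclusion.** The point holds in a narrow form. For a first Grade 3 event listed in Appendix G 3.6 that improves to below Grade 2 within 7 days and did not occur at 9 mcg/day, the protocol can be followed exactly and still restart pembrolizumab after an event for which its own appendix requires a permanent stop. The difference is at most 9 doses against 0, under the assumptions shown. The Grade 2 difference is real but secondary.

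A reader might go further and infer that DLT counts are distorted. The documents do not establish this. A Grade 3 event resolving in 7 days is exempt under the first DLT bullet. Whether a required stop counts under the other bullet ("Any clinically significant toxicity that precludes administration of the next scheduled dose for more than 14 days") depends on how that clause treats a discontinued dose, which the text does not say. Nor does the point touch the efficacy sample size or error rates. Priority: a minor safety clarification for a rare event of unstated frequency, with investigator judgment as a partial safeguard.

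**What to change.** Add to Section 5.7.1:

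> For events listed in Appendix G 3.6 judged immune-mediated and related to pembrolizumab: at Grade 3 or 4, permanently discontinue pembrolizumab and give corticosteroids per Appendix G 3.6, regardless of time to improvement; at Grade 2, follow Appendix G 3.6 (consider withholding pembrolizumab and prednisone). Blinatumomab continues to be managed under the Neurologic Toxicity table, which governs both drugs for all other neurologic toxicity, including seizure.

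This aligns the protocol with its appendix at both grades and does not mandate Grade 2 steroids. It keeps the blinatumomab safeguards: below Grade 2 for 3 days before restart, the 7-day limit, and off therapy if the event occurred at 9 mcg/day. It can go into the next amendment and adds no patients, visits or tests. The cost is that a few patients with a rapidly improving Grade 3 event lose further pembrolizumab. The DLT definition in Section 5.1.4 is left unchanged.
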